### 2.4 Sample Size Determination

No specific sample size calculations have been performed for this study.

It is planned to randomise at least 20 subjects in Cohort I and up to 10 subjects in Cohort II.

### 2.5 Randomisation and Blinding

Subjects will be allocated one of the following treatments: VIT-2763 QD or VIT-2763 BID or placebo. The randomisation allocation ratio will be 8:8:4 for Cohort 1 (adult NTDT subjects) and 4:4:2 for Cohort 2 (adolescent subjects) and the randomisation method will be interactive web response system (IWRS) RTSM from Medidata RAVE. The randomisation schedule was generated and maintained by Covance according to SOP number ST-SOP-001 version 06. The schedule and the seed will be sequestered until the study database is locked and the study is unblinded.

Table 3 presents the treatment group labels and table 4 presents the visit labels that will be used in all output.

Table 3 Study Treatments

Studied Treatment	Treatment Label
Active treatment 1	VIT-2763 QD
Active treatment 2	VIT-2763 BID
Placebo	Placebo

Adult and adolescent subjects will be randomised to receive either VIT-2763 QD or BID or placebo, at a dose of 120 mg for subjects with a body weight ≥60 kg or at dose of 60 mg for subjects with a body weight <60 kg.

Table 4 Study Visits

Visit Number (Title)	Visit Label
Visit 1 (Screening)	Screening
Visit 2 (Optional Screening)	Screening 2
Visit 3 (Day 1)	Baseline *
Visit 3 (Day 1)	Baseline 2h post-dose **
Visit 4 (Week 1)	Week 1
Visit 5 (Week 2)	Week 2
Visit 6 (Week 4)	Week 4
Visit 7 (Week 8)	Week 8
Visit 8 (Week 12)	EOT Week 12

Visit 9 (Week 16) EO	T Week 16
----------------------	-----------

\* Baseline is defined in section 5.1.2.

### 2.5.1 Interim Analysis

No formal interim analysis is planned.

A SRT will be instituted for this study in order to ensure ongoing safety of study subjects in this study.

### 2.5.2 Safety Review Team

For each cohort, blinded data of the first 10 subjects in Cohort I and the first 5 subjects in Cohort II will be reviewed by an SRT.

Data to be reviewed by the SRT are defined in the SRT charter version 1.0 date 16 March 2020. Tabulations and listings will be run on blinded data by Vifor Biostatistics Department (or other Vendors) and sent only to the SRT members.

For PK concentrations, dummy aliases will be used instead of subject identifiers. Timepoints where any subject has missing sample(s) will be removed entirely to prevent unblinding.

### 2.6 Study Endpoints

### 2.6.1 Primary Safety Endpoint(s)

[figure not shown]
- Reported or observed adverse events (AEs): by system organ class (SOC) and preferred term (PT) (MedDRA coded term), by severity and relation to study product in each treatment group.
- Reported or observed serious AEs (SAEs): by SOC and PT (MedDRA coded term), by severity and relation to study product in each treatment group.
- Changes in vital signs (supine systolic and diastolic blood pressure and pulse rate), clinical laboratory safety tests (haematology, serum biochemistry, coagulation, and urinalysis), 12-lead ECG, and physical examination findings.

### 2.6.2 Secondary Endpoint(s)

- Assessment of iron parameters (total serum iron, serum ferritin, serum transferrin, unsaturated iron binding capacity, calculated TSAT, from baseline over a 12-week period (absolute and change from baseline)).
- PK parameters: individual estimates of Cmax, clearance, distribution volume, AUC will be
  obtained using a population PK approach in adult and adolescent subjects combined with
  suitable mathematical/statistical analysis, using nonlinear mixed-effects modelling. Sparse
  sampling for determination of VIT-2763 plasma concentration following multiple dosing will be
  obtained from pre-dose trough to 3 or 4 hours post-dose at selected study visits.

\*\* For ECG, baseline value will be defined during Screening visit and assessment recorded at the Visit 3 (Day 1) will be presented as "Baseline 2h post-dose".

 Only in subjects who consent in writing to provide blood samples for biomarkers and genotyping, whole blood samples will be taken and stored for later determination of biomarkers and genotyping. The biomarker and pharmacogenetic endpoints will be defined at a later time point, taking into account further scientific and clinical data.

•

### 3 HYPOTHESES AND DECISION RULES

### 3.1 Statistical Hypotheses

No statistical hypotheses have been done since no formal sample size has been calculated.

### 3.2 Statistical Decision Rules

There is no formal statistical decision rule for this study, and all analyses are considered descriptive.

### 4 ANALYSIS SETS

In accordance with ICH E3 [1] and E9 [2] guidelines, the analysis sets are defined as follows:

### 4.1 Safety set

The safety set (SS) consists of all randomised subjects who have taken at least one dose of study medication. The subjects in the SS will be analysed based on the treatment they received, regardless of randomisation.

### 4.2 Full analysis set

The full analysis set (FAS) consists of all subjects who satisfy the following criteria:

- Randomised to treatment
- Received at least one dose of randomised treatment
- Had at least 1 post-baseline PD assessment

The FAS will be created in accordance with the Intent-To-Treat principles. The subjects in the FAS will be analysed based on the treatment that they were randomised to.

Subjects who received blood transfusion will be censored from their first transfusion date for the FAS. All efficacy and PK data considered as censored data will not be part of summary tables and figures but will be listed as other data and identified with a censor flag.

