12.9 Iron PD Evaluations

12.9.1 Secondary PD

Values by visit from baseline and changes from baseline by post-baseline visit for the iron parameters (total serum iron, ferritin, transferrin, calculated TSAT) and iron related

parameters will be summarised on overall subjects receiving VIT-2763, subjects receiving VIT-2763 by dose daily frequency and on subjects receiving placebo.

Values at each visit from baseline and changes from baseline at each post-baseline visit of the iron parameters (total serum iron, ferritin, transferrin, calculated TSAT) will be summarised on the same treatment groups.

Analyses will be performed on the FAS and the PPS. In case both analysis sets are identical, analysis will not be repeated.

If at least 1 subject is randomised in each body weight category, the summary statistics will be repeated by body weight category.

Observations will be treated as right-censored for subjects who complete the study treatment (Week 12) or prematurely withdraw prior to initiation of RBC transfusions, or any iron related pharmacological treatment.

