### 1 INTRODUCTION

This statistical analysis plan (SAP) describes the statistical methods to be used during the reporting and analyses of data collected under protocol VIT-2763-THAL-201 version 4.0 dated 12 April 2021.

This SAP should be read in conjunction with the study protocol and case report form (CRF). This version of the plan has been developed using the protocol dated 12 April 2021 and CRF dated 26 March 2021. Any further changes to the protocol or CRF may necessitate updates to the SAP. Statistical rationale and analysis methods specified in this document take precedence over those described in the protocol, should there be any differences.

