### 1.2 Changes from Protocol

A modified FAS has been defined and added in the section 4.4. A sensitivity analysis for efficacy will be performed on the modified FAS if more than 3 subjects are excluded due to major Covid-19 related protocol deviation.

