### 4.3 Per-protocol set

The per-protocol set (PPS) consists of all subjects who, in addition to the FAS criteria, had no major protocol deviation (as defined in the section 4.5 and finalised during the blind data review meeting).

The subjects in the PPS will be analysed based on the treatment that they were randomised to.

Subjects who received blood transfusion will be censored from their first transfusion date for the PPS. All efficacy and PK data considered as censored data will not be part of summary tables and figures but will be listed as other data and identified with a censor flag.

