## 5.9 Other Analyses

#### 5.9.1 Iron Pharmacodynamics Analyses

The values and change from baseline results of iron pharmadynamic parameters (serum iron, serum ferritin, serum transferrin, unsaturated iron binding capacity, calculated transferrin saturation) will be summarized and listed by treatment group and timepoints. No formal statistical tests are planned.

For each iron pharmadynamic parameters, the Baseline value is defined as the last non-missing measurement collected/during screening period.

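### The SAP censors efficacy data from first transfusion only; Protocol 12.9.1 also names iron-related drug treatment for the iron parameters, and the difference is undeclared

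*SAP*

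**What the plan says.** Protocol 12.9.1, the analysis section for the iron secondary endpoint, treats as right-censored the observations of subjects who complete Week 12 or who "prematurely withdraw prior to initiation of RBC transfusions, or any iron related pharmacological treatment". Two events are paired there: transfusion and iron-related drug treatment.

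The SAP keeps one of them. Section 4.2 reads "Subjects who received blood transfusion will be censored from their first transfusion date for the FAS", and section 4.3 reads "Subjects who received blood transfusion will be censored from their first transfusion date for the PPS". The consequence of censoring is given in 4.2: "All efficacy and PK data considered as censored data will not be part of summary tables and figures". Such values are listed with a flag.

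SAP 5.9.1 covers serum iron, ferritin, transferrin, UIBC and calculated TSAT. It says only that these "will be summarized and listed by treatment group and timepoints. No formal statistical tests are planned", with no censoring rule of its own.

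On precedence, SAP section 1 states: "Statistical rationale and analysis methods specified in this document take precedence over those described in the protocol, should there be any differences". SAP 1.2, which records departures from the protocol, opens "A modified FAS has been defined and added in the section 4.4" and otherwise mentions only the related sensitivity analysis.

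**The concern.** Chelators and iron preparations act directly on the variables that make up the preliminary-efficacy objective. The SAP accepts that transfusion makes later values unsuitable for the summary tables, yet gives no reason for treating iron-directed drugs differently, and a reader cannot tell whether the second event was left out on purpose.

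The situation is foreseeable. Exclusion criterion 2 admits subjects whose chelation stopped about four weeks before randomisation, and Protocol 2.2 anticipates that chelation may have to be added during the study. Where values are collected afterwards, the full analysis set would average them in with values that reflect study drug or placebo alone. The primary safety objective is not affected.

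**Working it through.** The plan gives no figure for this point, so the check is mainly a comparison of texts.

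**1. Events that censor**

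- Protocol 12.9.1 (iron parameters): transfusion, and iron-related drug treatment.
- Protocol 5.2 (note to criterion 2) and 6.8: transfusion only. Both are notes attached to the transfusion rule.
- SAP 4.2 and 4.3: transfusion only.
- SAP 5.9.1: no rule.
- SAP 1.2: no mention of censoring.

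Since the SAP prevails, the working rule is transfusion only.

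**2. Can affected values reach the tables?**

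- Concomitant chelation and iron therapy are prohibited (Protocol 6.8), and use of a non-permitted medication is on the list of reasons to stop study drug (Protocol 5.4.2). This limits the number of cases.
- Protocol 2.2 says only that patients who need chelation may have to be withdrawn, and 6.8 leaves the investigator free to prescribe needed care. Cases are therefore not ruled out.
- Protocol 5.4.2 keeps subjects on the visit schedule after drug is stopped for an adverse event, laboratory abnormality or illness. It does not say so for the non-permitted-medication item. Subjects who withdraw have the Visit 8 assessments if possible (Protocol 9.1.4).
- SAP 5.1.3 maps every assessment, planned or not, into an analysis window.

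So such values can exist, and those that do would enter the full-analysis-set tables.

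**3. Which sets are affected?** SAP 4.5 makes use of prohibited medication a major deviation for the per-protocol set, which removes the whole subject. The exposure lies in the full analysis set and in the modified set of SAP 4.4, which is drawn from it.

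**4. Weight of one subject.** If iron treatment changes one subject's value by X, an arm mean over n subjects moves by X/n.

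- Inputs: at least 20 adults at 8:8:4 (Protocol 12.3).
- Active arm: 1/8 = 12.5%.
- Placebo arm: 1/4 = 25%.

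SAP 5.1 repeats the summaries by body-weight category, where n is smaller.

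**5. Chance of at least one case.** The documents give no rate of starting chelation or iron, so p is an assumption. The chance is 1 − (1 − p)^N, with N = 20 (minimum Cohort I) or N = 36 (planned randomised total).

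| Assumed p | N = 20 | N = 36 |
|---|---|---|
| 2% | 1 − 0.98^20 = 33% | 1 − 0.98^36 = 52% |
| 5% | 1 − 0.95^20 = 64% | 1 − 0.95^36 = 84% |
| 10% | 1 − 0.90^20 = 88% | 1 − 0.90^36 = 98% |

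**The case against.** **The protocol sentence is not a clear exclusion rule.** Read literally, it censors subjects who finish or leave before either event, which is time-to-event language. It does not plainly say that later values leave the summaries. The protocol's other censoring statements name transfusion alone, and the SAP follows those. This stands: a reader might infer that the SAP broke a clear protocol rule, and the documents do not support that. What remains is that the iron analysis section pairs the two events and the SAP, which should have clarified the sentence, carried over only one.

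**The per-protocol set already deals with it.** Largely true. It would be wrong to infer that both sets are equally exposed. Cover may not be complete, because treatment given under the investigator's discretion in Protocol 6.8 need not be classed as a deviation.

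**The full analysis set follows intent-to-treat, and censoring at chelation can be informative.** Keeping values after an added treatment is a defensible choice if made openly. But the SAP has already left that principle by censoring at transfusion, and it does not explain the different treatment of drugs that act on the endpoint. The point about informative censoring is fair, and is the reason for a sensitivity table.

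**There are no tests, and cases may be none.** Both hold. A reader might infer that affected values are bound to be collected and that the comparison with placebo is biased. The documents show only that this can happen.

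**Text is blacked out.** Parts of SAP 5.6 and of the sentence on analysis sets in SAP 5.1.6 cannot be read. A rule there cannot be excluded; none appears in the readable text.

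**Conclusion.** The concern holds as an undeclared mismatch with a limited consequence. Under the readable SAP, iron values obtained after chelation or iron therapy begins stay in the full-analysis-set and modified-set summaries of the secondary endpoint.

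The size cannot be stated in units of any iron marker, because neither the frequency nor the effect X is given. One affected subject would move an active-arm mean by X/8 or the placebo mean by X/4, assuming Cohort I at its minimum of 20 with every subject contributing at that visit. Arms may turn out larger or smaller. The rates of 2% to 10% are illustrative only.

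A related gap should be closed at the same time. SAP 4.2 censors efficacy and PK data, while the iron parameters sit under other analyses in 5.9.1 and 5.6.2 calls secondary efficacy not applicable. The SAP therefore does not say outright that even the transfusion rule reaches them. The secondary objective, which describes the iron markers as preliminary efficacy, suggests that it does.

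**What to change.** In SAP 4.2 and 5.9.1, state that serum iron, ferritin, transferrin, UIBC and calculated TSAT are censored from the earlier of the first RBC transfusion after first dose and the first iron-related drug treatment after first dose, the latter meaning chelation or iron therapy. Use the existing censor flag. State that the second trigger does not apply to PK concentrations, since Protocol 12.9.1 concerns iron parameters only; adding it to the general sentence in 4.2 would remove PK data as well.

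Take the date from the concomitant-medication page. SAP 5.2 already identifies chelators by ATC code V03AC; a code list for iron preparations has to be added. Say how a partial start date sets the censoring date, because SAP 5.1.9 imputes to the first day of the month or year.

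Show the full-analysis-set iron summary without the second trigger as a sensitivity table. If the omission was intended, record it with its reason in SAP 1.2 and present the summaries both ways. In either case, reconcile the wording of Protocol 12.9.1 with Protocol 5.2 and 6.8.

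The cost is a short SAP edit, one derived date and one extra table. A few values would move from tables to listings, and censoring at chelation may be informative; the sensitivity table lets a reader judge how much that matters.

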5.2 Inclusion Criteria

The following inclusion criteria must be met for each subject:

- 1. Documented diagnosis of NTDT, including a β -thalassaemia intermedia-phenotype.
- 2. NTDT is defined as subjects having received <5 units of red blood cells (RBCs) during the 24-week period prior to randomisation/first drug administration of VIT-2763 or placebo (Day 1; 1 unit is defined as 200 to 350 ml of transfused packed RBCs and last RBC transfusion must have been received ≥14 days prior to randomisation).
 - Note: Subjects who are supposed to receive RBC transfusions after randomisation in the Investigator's opinion, and according to local practise, and having received at least 1 dose of VIT-2763, may be considered to stay on study treatment for safety reasons, and in case there are no tolerability concerns. Subjects will be censored for secondary efficacy.
- 3. Male and female adult* NTDT subjects, 18-65 years of age inclusive (Cohort I only) at time of screening.

- * Following section in italics is applicable for dedicated Thailand site(s) as per local EC/IRB guidance:
- 3. Male and female adult NTDT subjects, 20-65 years of age inclusive (Cohort I only) at time of screening.
- 4. Male and female adolescent* NTDT subjects, 12-17 years of age inclusive (Cohort II only) at time of screening.
- * Following section in italics is applicable for dedicated Thailand sites(s) as per local EC/IRB guidance:
- 4. Male and female adolescent NTDT subjects, 12-19 years of age inclusive (Cohort II only) at time of screening.
- 5. Subjects must have a mean baseline Hb \leq 11 g/dl, based on at least 2 consecutive measurements \geq 1 week apart within 6 weeks prior to randomisation/baseline.
 - Note: If obtained Hb values show more than 10% relative difference and more than 1.0 g/dl absolute change between the highest and lowest value, the subject must be excluded. If there is 1 retrospective Hb value available for the subject at maximum of 2 weeks prior to screening (Day -28), the Hb value can be taken into consideration. A subject not meeting this criterion would be excluded but can be rescreened at maximum 2 times at a later time point.
- 6. Ability to understand the requirements of the study and abide by the study restrictions, and agreement to return for the required assessments.
- 7. Ability to swallow a capsule Size 0, to be assessed during the screening visit.

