12.12 Other Evaluations

12.12.1

Values by visit from baseline and changes from baseline by post-baseline visit for Hb, reticulocytes, amylase, bicarbonate, eGFR, will be summarised on overall subjects receiving VIT-2763, subjects receiving VIT-2763 by dose daily frequency and on all subjects receiving placebo.

The counts and percentages of subjects achieving an increase in Hb \geq 1.0 g/dl and the ones achieving an increase in Hb \geq 1.5 g/dl will be provided by visit on the same treatment groups.

If at least 1 subject is randomised in each body weight category, the summary statistics will be repeated by body weight category.

Analyses will be performed on the FAS and the PPS. In case both analysis sets are identical, analysis will not be repeated.

Values by visit from baseline and changes from baseline by post-baseline visit for will be summarised on overall subjects receiving VIT-2763, on subjects receiving VIT-2763 by dose daily frequency and on all subjects receiving placebo.

Analyses will be performed on the FAS and the PPS. In case both analysis sets are identical, analysis will not be repeated.

If at least 1 subject is randomised in each body weight category, the summary statistics will be repeated by body weight category.

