### 5.1.8 Analysis of Subgroups

The following subgroups will be considered:

- Body weight at screening: <60 kg/ ≥ 60 kg

- Gender: Male/Female
- Race: American Indian or Alaska Native/Asian/Black or African American/Native Hawaiian or Other Pacific Islander/White/Other. Each race category will be part of subgroup analysis only if there is at least one subject in.

In case of imbalance between treatment groups regarding baseline characteristics, other subgroup analyses may be performed.

Following outputs will be repeated in each subgroup:

- Table 14.2.1.1.1 Summary statistics of other iron related parameters over time
- Table 14.2.1.5.1 Summary Statistics of Increase from Baseline in Haemoglobin by Visit
- Table 14.3.1.1.1 Overall Summary of Adverse Events
- Table 14.3.1.2.1 Treatment-emergent Adverse Events by System Organ Class and Preferred Term
- Table 14.3.1.3.1 Serious TEAEs by System Organ Class and Preferred Term
- Table 14.3.1.5.1 Serious TEAEs related to study medication by System Organ Class and Preferred Term

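### The SAP does not settle how a transfused subject counts in the haemoglobin-response percentages, and its date-based censoring can drop samples drawn before a same-day transfusion

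*SAP*

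**What the plan says.** **Censoring.** SAP 4.2 states "Subjects who received blood transfusion will be censored from their first transfusion date for the FAS", and SAP 4.3 has the matching sentence, "Subjects who received blood transfusion will be censored from their first transfusion date for the PPS". The consequence is the same in both sections: "All efficacy and PK data considered as censored data will not be part of summary tables and figures but will be listed as other data", with a flag. The rule is keyed to a date, not a clock time, and is not limited to transfusions after randomisation. SAP 4.2 also says: "The FAS will be created in accordance with the Intent-To-Treat principles".

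**Protocol basis.** Protocol 5.2 says of subjects transfused after randomisation: "Subjects will be censored for secondary efficacy". It gives no start point and no handling rule. Protocol 5.2 and 6.8 allow such a subject to be considered for staying on study treatment.

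**Outputs affected.** Protocol 12.12 asks for by-visit Hb values and changes and for "The counts and percentages of subjects achieving an increase in Hb" of at least 1.0 and at least 1.5 g/dl, on the FAS and PPS. SAP 5.1.8 lists "Table 14.2.1.5.1 Summary Statistics of Increase from Baseline in Haemoglobin by Visit" among the outputs to be repeated by subgroup. That table sits in the 14.2 series, apart from the 14.3 adverse event tables, so reading Hb increase as efficacy data is natural.

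**Denominator.** SAP 5.1.1, under categorical variables, first bases percentages on the number of values available. It then bases them on all subjects in the randomised treatment group, with an exception for safety-set outputs.

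**The concern.** Removing values that donor blood may have raised is sensible for iron markers and for mean Hb. A responder percentage is different. A subject transfused because Hb was low has not achieved a rise in Hb, and that should show in the table. If the subject disappears from both numerator and denominator, the exclusion depends on the outcome, which does not fit the Intent-To-Treat claim in SAP 4.2. No visible text says that a transfused subject is a non-responder.

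The PPS is unlikely to fill the gap. Transfusion during the study is prohibited (Protocol 6.8), and use of prohibited therapy is a major deviation (SAP 4.5), so transfused subjects may be outside the PPS altogether.

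The date rule raises a second problem. Under Protocol 9.1.4 the local Hb result must be available before the subject leaves the hospital, and central haematology is drawn at the same visits. A transfusion prompted by a visit result could therefore fall on the visit date. A literal reading would then discard the low Hb that prompted it, together with that day's iron and PK samples, even if all were drawn before any donor blood was given.

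**Working it through.** The plan gives no transfusion rate, Hb response rate or estimate of the effect of censoring, so there is no planned figure to reproduce. The counts below are assumptions placed on the planned allocation.

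**Inputs.** Cohort I at its minimum of 20 subjects, allocated 8:8:4 (Protocol 12.3): 8 + 8 = 16 active and 4 placebo. Assumed responders: 4/16 active and 1/4 placebo, 25.0% in each. Assumed: no transfused subject was a responder.

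**Formulas.** With r responders, n subjects and t transfused subjects before the visit:
- all randomised subjects as denominator: r/n
- available values as denominator: r/(n − t)

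**One arm of 8 with 2 responders.** Available values: t = 0 gives 2/8 = 25.0%; t = 1 gives 2/7 = 28.6%; t = 2 gives 2/6 = 33.3%. All subjects: 2/8 = 25.0% throughout.

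**Active versus placebo.**

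| Transfused (active, placebo) | All subjects | Available values | Difference, available values |
|---|---|---|---|
| 0, 0 | 25.0% vs 25.0% | 4/16 = 25.0% vs 1/4 = 25.0% | 0 |
| 2, 0 | 25.0% vs 25.0% | 4/14 = 28.6% vs 1/4 = 25.0% | +3.6 points |
| 0, 1 | 25.0% vs 25.0% | 4/16 = 25.0% vs 1/3 = 33.3% | −8.3 points |
| 2, 1 | 25.0% vs 25.0% | 4/14 = 28.6% vs 1/3 = 33.3% | −4.8 points |
| 4, 1 | 25.0% vs 25.0% | 4/12 = 33.3% vs 1/3 = 33.3% | 0 |

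The denominator decides whether there is any distortion, and the arm with the higher transfusion rate decides its sign.

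**Why later values should not simply be put back.** If 2 active subjects were transfused and each then showed a rise of at least 1.0 g/dl, the table would read (4 + 2)/16 = 37.5% against 25.0%. Donor blood would have created the responders.

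**Upper bound for mean Hb change.** Take true changes as normal with mean 0 and SD σ, and suppose every value below −c is lost. The remaining mean is σ·φ(c/σ)/Φ(c/σ). For assumed σ of 0.8 to 1.0 g/dl and c of 1.0 to 1.5 g/dl:
- σ = 0.8, c = 1.5: +0.06 g/dl
- σ = 1.0, c = 1.5: +0.14 g/dl
- σ = 0.8, c = 1.0: +0.16 g/dl
- σ = 1.0, c = 1.0: +0.29 g/dl

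This is a worst case. It needs every triggering sample to fall on the transfusion date and no earlier value to fill the visit.

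**The case against.** **The denominator.** The strongest reply is that the second sentence in SAP 5.1.1 already solves the problem. With all randomised subjects as the denominator, a censored subject counts as not having achieved the rise, and the percentage is 25.0% in every scenario above. That is correct, but the other sentence stands in the same subsection and gives a different answer from the same data. The choice should not be left to programming.

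**Redaction.** SAP 5.6.3, on exploratory efficacy, is blacked out and could hold a non-responder rule or a sensitivity analysis. That limits the point to the visible text. It does not remove the conflict in 5.1.1 or the date wording in 4.2 and 4.3, both of which are visible.

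**Falling Hb shows elsewhere.** Values before the transfusion date stay in. Unscheduled assessments are remapped into visit windows (SAP 5.1.3), so an earlier value may supply the visit. Censored values are listed with a flag, safety-set haematology has no stated transfusion censoring, and clinically relevant worsening of anaemia is reported as an adverse event (Protocol 8.1.2). All of this stands, and safety reporting is not compromised. It does not make the response percentage itself well defined.

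**Materiality.** Hb response is neither a primary nor a secondary endpoint, transfusions are not expected during treatment (Protocol 2.2), and nothing is tested. This also stands and limits the consequence. In arms this small, though, one subject visibly moves a percentage.

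**Same-day samples.** The SAP gives no within-day rule, so deletion of a sample drawn before a same-day transfusion is the literal reading rather than a stated intention.

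**Conclusion.** The SAP needs correction on two points: the responder status and denominator for transfused subjects, and samples drawn before a transfusion on the same day.

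The size depends on assumptions. On available values, one transfusion in an arm of 8 with 2 responders moves 25.0% to 28.6%, and one in 4 placebo subjects with 1 responder moves 25.0% to 33.3%. On all randomised subjects the shift is zero. Type I error and power are not affected, because the analyses are descriptive.

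A reader might infer that the rule makes the drug look better, particularly as it restricts iron supply to erythropoiesis. The documents do not support that. The rule covers every arm, no transfusion rates are given, and in the scenarios above a single placebo transfusion makes the drug look worse by 8.3 points. Nor can one conclude that transfused subjects necessarily drop out of the percentages, since one of the two denominators keeps them. The 0.06 to 0.29 g/dl range for mean Hb is an upper bound under assumed values, not an expected bias.

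**What to change.** 1. In SAP 4.2 and 4.3, for the tables of Hb increase of at least 1.0 and 1.5 g/dl, count a subject as a non-responder at every visit after the first post-randomisation transfusion. Use one fixed denominator: all FAS (or PPS) subjects in the randomised group. Reconcile the two sentences in SAP 5.1.1 accordingly.
2. In both sections, start censoring after the first post-randomisation transfusion instead of from the first transfusion date, and keep samples drawn before the transfusion on the same day. Naming post-randomisation also prevents a transfusion before entry from triggering the rule; Protocol 5.2 admits subjects with fewer than 5 units in the preceding 24 weeks.

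Leave the censoring of later iron and mean Hb values as it is.

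The cost is SAP wording and a few lines of programming. No new assessments are needed, though same-day samples need a documented order relative to the transfusion. Compared with the available-values reading, item 1 can only leave response percentages the same or lower them. The fixed denominator also keeps subjects whose value is missing for other reasons, which should be stated under the table.
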